In a recent Cochrane review on the comparison of self-administered survey questionnaire responses collected using mobile apps versus other methods it was concluded that there are no data available on response rates. We will attempt to address this question.

RESEARCH DESIGN AND METHODS

Briefly describe study design and anticipated enrollment, i.e., number of subjects to be enrolled by researchers study-wide and by Partners researchers. Provide a brief summary of the eligibility criteria (for example, age range, gender, medical condition). Include any local site restrictions, for example, “Enrollment at Partners will be limited to adults although the sponsor’s protocol is open to both children and adults.”

All Patient Gateway naïve patients aged 18 years or older able to consent for themselves, admitted to the hospital for an orthopaedic condition with the need for outpatient follow-up and access to the internet or a smartphone will be invited to participate in this study. Exclusion criteria will be patients unable to consent for themselves, inability to communicate in English, and no possession of a smartphone.

We will collect 240 patients; 120 in each group. Existing follow-up is assumed to be close to 70%, to detect a 15% difference at 95% CI, N=240.

Briefly describe study procedures. Include any local site restrictions, for example, “Subjects enrolled at Partners will not participate in the pharmacokinetic portion of the study.” Describe study endpoints.

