Eligible patients will be randomized into two groups; one group that is enrolled while an inpatient and another group that is just provided information about how to enroll. All patients eligible for participation will be approached during their hospital stay and asked for consent. Patients will be cluster randomized by week and after consenting, they will be assigned to the treatment arm randomized to that specific week. For intervention group, an explanation on the app will be provided by a trained research staff member and they will be fully enrolled in the app in the presence of this research staff member. In the period between hospital discharge and follow-up, patients using the Gateway app will be requested to fill out a survey on their personal device and will receive a notification of their upcoming appointment. We will monitor when patients return to clinic for their first, 90-day, and 1-year follow-up outpatient appointments. At 90 day and 1 year follow-up outpatient appointments, patients from both groups will be invited to complete a survey on a hospital owned tablet device per standard clinic protocol. In addition to the standard survey, two brief questionnaires on satisfaction with the electronic application and satisfaction with overall care

will be provided at the end of the regular survey (if already completed over the app; just the satisfaction questions will be administered).

Descriptive statistics will be used for demographic data. Logistic regression will be used for binary outcome data.

For studies involving treatment or diagnosis, provide information about standard of care at Partners (e.g., BWH, MGH) and indicate how the study procedures differ from standard care. Provide information on available alternative treatments, procedures, or methods of diagnosis.

Not applicable as this study does not alter treatment or diagnosis in any way.

Describe how risks to subjects are minimized, for example, by using procedures which are consistent with sound research design and which do not unnecessarily expose subjects to risk or by using procedures already being performed on the subject for diagnostic or treatment purposes.

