When specimens or data collected by research collaborators outside Partners will be sent to Partners investigators, indicate from where the specimens/data will be obtained and whether the specimens/data will contain identifiers that could be used by Partners investigators to link the specimens/data to individual subjects. When appropriate, submit documentation of IRB approval and a copy of the IRB-approved consent form from the institution where the specimens/data were collected.

No specimens/data will be received from sites outside of partners for future use.

Statistical analysis, study size

Descriptive statistics were used for demographic data. Differences between groups were assessed using the chi-square or Fisher's exact test for categorical variables and the t-test and/or analysis of variance (ANOVA) for continuous variables. Demographic or treatment factors associated with improved follow-up or EPP use were assessed using forward stepwise logistic regression modeling to avoid overfitting. We also performed a sub-group analysis assessing the effect of patient race and average median income. A robustness analysis exploring the likelihood of enrolling in an EPP or completing follow-up in all patients was also performed. Significance was set at $P < 0.05$. Stata software, version 14 (StataCorp), was used for all analyses.

An a priori power analysis was completed to determine sample size, we assumed an existing follow-up rate of 70%, and to detect an ~10% difference in follow-up with an alpha of 0.05, we calculated an approximate sample size of 200 patients distributed equally between both groups.

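### The exploratory analysis of app enrolment covers all patients although staff enrol the whole intervention arm, so only controls inform who chooses to enrol

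*Combined protocol and SAP*

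**What the plan says.** Under Research Design and Methods, nobody has the app at entry: eligibility begins with "All Patient Gateway naïve patients aged 18 years or older able to consent for themselves". Enrolment then differs by arm. For the intervention group, after an explanation of the app, "they will be fully enrolled in the app in the presence of this research staff member". The comparator is "another group that is just provided information about how to enroll". Enrolment is therefore a delivered procedure in one arm and a patient's own decision in the other.

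The section Statistical analysis, study size names two analyses that touch on the app. One is about enrolling: "A robustness analysis exploring the likelihood of enrolling in an EPP or completing follow-up in all patients was also performed". The other is about use: "Demographic or treatment factors associated with improved follow-up or EPP use were assessed using forward stepwise logistic regression modeling to avoid overfitting". Neither is restricted to controls. The section does not say whether arm is a term in either analysis, does not separate enrolling from using, and does not spell out EPP.

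**The concern.** An analysis of who enrols is informative only where patients can either enrol or not. If staff enrol every intervention patient, half the sample has the same outcome whatever the patient's age, race or income. What follows depends on a modelling choice that the plan leaves open.

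- **Arm left out.** The fixed half dilutes every patient-level association with enrolment.
- **Arm included.** The arm coefficient has no finite maximum-likelihood estimate, and an odds ratio for arm would restate the design.

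The same section plans a subgroup analysis by race and median income. It does not say that enrolment is the outcome there. If those factors were examined for enrolment in pooled data without arm, real differences in who takes up the app unaided could look small or absent.

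**Working it through.** **Arm size.** The protocol summary states "We will collect 240 patients; 120 in each group", for follow-up of 70% against a 15-point improvement. With two-sided alpha 0.05 and power 80% (neither sidedness nor power is stated), n per arm = [1.96·√(2·0.775·0.225) + 0.8416·√(0.70·0.30 + 0.85·0.15)]² / 0.15² = (1.157 + 0.489)² / 0.0225 ≈ 121, or 242 in total. The 240 is reproduced to within rounding and is not disputed here. The statistics section gives another total ("we calculated an approximate sample size of 200 patients distributed equally between both groups"). Using 100 per arm leaves the odds ratios below unchanged and lowers power.

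**Assumptions not in the documents.** The self-enrolment rate in controls is not given, so a range is shown. The predictor is binary with 50% prevalence and a true odds ratio of 3 in controls. Intervention enrolment is 100% unless stated.

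**Case 1: arms pooled, no arm term.** Let p0 and p1 be control enrolment without and with the predictor, solved so that (p0 + p1)/2 is the self-enrolment rate and the odds ratio is 3. Pooled enrolment is m = (p + 1)/2 in each predictor group, so the risk difference is exactly halved.

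| Control self-enrolment | p0, p1 | m0, m1 | Pooled odds ratio |
|---|---|---|---|
| 20% | 11.7%, 28.3% | 55.8%, 64.2% | 1.42 |
| 30% | 18.9%, 41.1% | 59.4%, 70.6% | 1.64 |
| 50% | 36.6%, 63.4% | 68.3%, 81.7% | 2.07 |

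For the 30% row: (0.7056/0.2944) / (0.5944/0.4056) = 2.397/1.466 ≈ 1.64. Simulated power at 30% is about 79% in the 120 controls and about 41% in all 240 pooled.

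A weaker predictor behaves in the same way. With a true odds ratio of 2.5 and self-enrolment of 20%, 40% and 60%, the pooled odds ratio is 1.34, 1.68 and 1.99. Power by the two-proportion formula is 49%, 68% and 68% in controls, against 20%, 45% and 55% pooled.

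Dilution does not need perfect enrolment. With 95% of the intervention arm enrolled, the pooled odds ratio for a true value of 3 at 30% self-enrolment is 1.61.

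**Case 2: arm in the model.** At 30% self-enrolment the counts enrolled and not enrolled are 120 and 0 (intervention) and 36 and 84 (control). The arm odds ratio is (120 × 84)/(0 × 36), which is infinite. One simulated fit gave an arm coefficient of 26.7 with a standard error of about 39,000. As that coefficient grows, the intervention patients' likelihood contributions tend to 1 and drop out, so the predictor estimates become the control-only ones. Simulation agrees: the median predictor odds ratio is about 3.1 and power is 79%.

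If 95% are enrolled, unrelated to the predictor, the arm odds ratio is finite but very large: (114/6)/(36/84) = 44.3. The arm-adjusted pooled model then gives a predictor odds ratio of roughly 2.5 and power of 68%, against 79% for controls only.

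**The case against.** The strongest reply is that dilution needs a model without arm, and the plan specifies no such model. The stepwise analysis admits treatment factors as candidates, which plausibly include arm. In the scenario above arm alone was significant in all 1,000 simulated datasets, so stepwise selection would take it if offered. A reader might infer that the analysis as written must give attenuated predictors. The documents do not support that: with arm in the model and full enrolment, nothing about the predictors is lost.

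A reader might also infer that the stepwise model has an outcome fixed by design. That does not follow either. Its outcome is EPP use, and the study procedures speak separately of patients using the app between discharge and follow-up. If use means later activity, staff enrolment does not determine it.

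The robustness analysis is described in a single sentence. It names no covariates and no regression, and it could be no more than enrolment proportions by arm. The phrase about all patients could also attach only to completing follow-up. Finally, the protocol describes an enrolment procedure, not an achieved rate. If about 93% of the intervention arm were enrolled and the same odds ratio of 3 applied there, the arm-adjusted pooled model would have 89% power against 79% for controls only.

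All of this stands as a limit on the point. What remains is that the plan sets enrolling as an outcome, on its natural reading in all patients, without restricting it to controls or saying what happens to arm.

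**Conclusion.** The point holds in a conditional form, as a cheap improvement to an exploratory analysis. Read with EPP as Patient Gateway, intervention-arm enrolment is set by the design and carries little or no information on who chooses to enrol.

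Pooling without arm would shrink a true odds ratio of 3 to about 1.4 to 2.1 over self-enrolment of 20% to 50% and, at 30%, cut power from about 79% to about 41%. These sizes rest on the assumed odds ratio, predictor prevalence and self-enrolment rates. Including arm removes the dilution at 100% enrolment, but the infinite arm odds ratio should not be reported or interpreted as a finding.

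It would be too strong to conclude that the trial's main results are at risk. Neither stated aim concerns predictors of enrolment, and the randomised comparison of clinic follow-up and survey completion is not affected.

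**What to change.** In the section Statistical analysis, study size:

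- Define EPP, and treat enrolling and using as separate outcomes.
- Model predictors of self-enrolment in the control (information-only) arm only.
- Report enrolment by arm descriptively, as a check that the intervention was delivered, with no odds ratio for arm.
- Define EPP use as app activity after discharge, and model it in both arms with arm forced into the model and not left to stepwise selection.

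The cost is wording; no new patients are needed, and the only extra data would be a record of app activity if none is already kept. The enrolment model uses half the sample, but at full enrolment the other half adds nothing on this outcome. If intervention enrolment falls short of 100%, the control-only model sets aside the few patients not enrolled despite assistance; describe them separately.

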Protocol Summary and Statistical Analysis Plan

Does inpatient enrollment into a patient communication app (Patient Gateway) result in improved follow-up and survey completion rates after orthopaedic trauma?

NCT2017P001594

Version Date 03/07/2018

**PARTNERS HUMAN RESEARCH COMMITTEE
PROTOCOL SUMMARY**

Answer all questions accurately and completely in order to provide the PHRC with the relevant information to assess the risk-benefit ratio for the study. Do not leave sections blank.

PRINCIPAL/OVERALL INVESTIGATOR

[name], MPH, FRCSC

PROTOCOL TITLE

Does inpatient enrollment into a patient communication app (Patient Gateway) result in improved follow-up and survey completion rates after orthopaedic trauma?

FUNDING

Department Funding

VERSION DATE

3/7/2018

SPECIFIC AIMS

Concisely state the objectives of the study and the hypothesis being tested.

This study aims to:

1. To determine if inpatient enrollment into a patient communication app (Patient Gateway) improves clinic follow-up of orthopaedic trauma patients.
2. To determine if inpatient enrollment into a patient communication app (Patient Gateway) improves survey completion rates after orthopedic trauma.

BACKGROUND AND SIGNIFICANCE

Provide a brief paragraph summarizing prior experience important for understanding the proposed study and procedures.

Follow-up in trauma is historically poor. As a result, outcomes from trauma are difficult to collect via surveys and are often significantly influenced by selection bias. Patient interaction apps like Patient Gateway are thought to facilitate greater participant involvement and adherence to treatment regimens. We explored if inpatient enrollment into Patient Gateway would improve clinic follow-up rates. Increasing follow-up rates could improve the quality of care delivered.

In addition, self-administered survey questionnaires are an important data collection tool in clinical practice, public health research and epidemiology. However, survey completion rates are typically poor in orthopaedic trauma.

With the evaluation of modern technology, electronic applications are being increasingly used in both hospital and personal settings. In our outpatient clinic, questionnaires to measure outcomes and monitor quality of care are

administered by staff members using hospital owned tablet devices. Recently, applications to complete these surveys on personal devices have been developed.

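### Clinic follow-up leads the plan, but no visit or combination is named primary, the 70% rate belongs to no visit, and the stated tests do not mention randomisation by week

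*Combined protocol and SAP*

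**What the plan says.** All the text is in the combined protocol and SAP.

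- **Specific Aims.** The first aim asks whether inpatient enrolment "improves clinic follow-up of orthopaedic trauma patients". The second asks the same of survey completion. Neither gives a time point, and neither is called primary.
- **Research Design and Methods, sample size.** "Existing follow-up is assumed to be close to 70%, to detect a 15% difference at 95% CI, N=240", with 120 per group. No visit is attached to the 70%, and no power is stated.
- **Research Design and Methods, procedures.** The form asks for the study endpoints here. The answer on attendance is "We will monitor when patients return to clinic for their first, 90-day, and 1-year follow-up outpatient appointments". Allocation is described as "Patients will be cluster randomized by week and after consenting, they will be assigned to the treatment arm randomized to that specific week", and the analysis as "Logistic regression will be used for binary outcome data".
- **Statistical analysis, study size.** Group differences are assessed by chi-square or Fisher's exact test for categorical variables. The modelling is described as "Demographic or treatment factors associated with improved follow-up or EPP use were assessed", by forward stepwise logistic regression. A robustness analysis is described as "exploring the likelihood of enrolling in an EPP or completing follow-up in all patients". The significance level is 0.05. The second sample-size statement again has "we assumed an existing follow-up rate of 70" per cent, still with no visit, but now for a difference of about 10% and about 200 patients.

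**The concern.** Follow-up could mean the first visit, the 90-day visit, the 1-year visit, any of them or all of them, and the plan does not say which. Two consequences follow whatever was intended. First, the definition can be fixed, even in good faith, after the results are known. Second, neither sample-size statement can be matched to a result, because the endpoint with the 70% rate is unknown. A third consequence is conditional: if each visit is tested at 0.05 and any success is read as better follow-up, the 0.05 is not held.

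A separate problem affects whichever endpoint is chosen. The week is the randomised unit, but none of the stated tests mentions it. If patients admitted in the same week resemble one another, tests that treat them as independent use standard errors that are too small.

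**Working it through.** **1. The plan's own figure.** Inputs: 70%, a 15% difference and 120 per group (Research Design and Methods). Assumptions: the difference is absolute (70% vs 85%), the test is two-sided at 0.05 and power is 80%. With the pooled two-proportion formula and mean rate 0.775:

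n per arm = [1.960·√(2·0.775·0.225) + 0.842·√(0.70·0.30 + 0.85·0.15)]² / 0.15² = [1.960·0.5906 + 0.842·0.5810]² / 0.0225 ≈ 120.5, so 121 per arm and 242 in all.

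This agrees with 240. Power at 120 per arm is 79.8%, for one binary endpoint and independent patients.

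**2. The second statement.** For 70% vs 80% with 100 per arm, the standard error is √(0.375/100) = 0.0612 under the null and √(0.37/100) = 0.0608 under the alternative. Power = Φ[(0.10 − 1.960·0.0612)/0.0608] = Φ(−0.33) ≈ 37%. For 80% power the same formula as in step 1 needs 588 patients. The two statements conflict, and the second does not reproduce.

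**3. Why the visit matters.** For a 15-point gain with 120 per arm, before clustering (the 50% and 80% rates are assumed, as the plan gives no rates by visit):

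| Control rate | Power | N for 80% power |
|---|---|---|
| 50% | 65.4% | 340 |
| 70% | 79.8% | 242 |
| 80% | 94.5% | 152 |

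**4. If, and only if, three visits are tested separately and any one counts.** Take no true effect, three equicorrelated normal statistics and each test of true two-sided size 0.05. At correlation 0 the chance of a false claim of benefit is 1 − 0.975³ = 7.3%, and of a false positive in either direction 1 − 0.95³ = 14.3%. The other values come from numerical integration. The plan gives no correlations.

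| Correlation | False benefit | Either direction |
|---|---|---|
| 0 | 7.3% | 14.3% |
| 0.5 | 6.3% | 12.5% |
| 0.7 | 5.5% | 10.9% |
| 0.9 | 4.2% | 8.4% |

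For one test these are 2.5% and 5%.

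**5. Randomisation by week.** Design effect DE = 1 + (m − 1)·ICC, for m patients per week. The true size of a test that ignores week is 2·[1 − Φ(1.96/√DE)]. Power is for 70% vs 85% with 120 per arm and variances multiplied by DE. The plan gives neither m nor the ICC.

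| m | ICC | DE | Size if week ignored | Power allowing for week |
|---|---|---|---|---|
| 5 | 0.01 | 1.04 | 5.5% | 78.3% |
| 5 | 0.05 | 1.20 | 7.4% | 72.2% |
| 10 | 0.01 | 1.09 | 6.0% | 76.3% |
| 10 | 0.05 | 1.45 | 10.4% | 63.9% |

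At these cluster sizes 240 patients make 240/5 = 48 or 240/10 = 24 weeks in total, few enough for small-sample corrections to matter.

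**The case against.** The strongest reply is that the plan never says the visits will be tested separately, or that one significant visit would count as success. Its wording leans towards a single measure: each sample-size statement uses one rate, and the three visits are said only to be monitored, which describes data collection. That stands. A reader might infer that the trial runs at a 14.3% false-positive rate. The documents do not support this, because the figure needs three independent tests, an any-visit rule and errors counted in both directions. What survives is that a single measure still has to be defined, and it is not.

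Three further points are fair.

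- Clustering is a different defect. It would remain with a perfectly defined endpoint, and its size rests on assumed values. It is therefore kept separate here.
- A composite of visits would close the gap as well as a single visit would. Nothing in the plan singles out the 90-day visit.
- Treating survey completion as secondary would be an inference. The title and aims give it equal billing, and only list order and the sample-size basis put attendance first.

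A reader might also take the past tense of the statistical section as evidence that the endpoint was chosen after the results were known. It is not evidence of that. It is a reason to ask whether outcomes by arm had been seen.

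**Conclusion.** The omission is certain: no visit or combination is primary, and the 70% belongs to none. The endpoint can therefore be chosen after the data are seen, and neither power calculation can be tied to a result. Inflation across visits is conditional. It is about 4.2% to 7.3% against 2.5% for a false claim of benefit under the any-visit rule with assumed correlations of 0.9 to 0, and nil for one pre-defined measure.

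The silence on week is also certain, but its size is not. True size is about 5.5% to 10.4% for a nominal 5% test that ignores week, under the assumed cluster sizes and ICCs.

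It would be wrong to conclude that 240 was miscalculated. It reproduces for 70% vs 85% at about 80% power before clustering. The faults are that its endpoint is unnamed, that it makes no allowance for week, and that the second statement contradicts it. The plan should be corrected on these points; they do not by themselves invalidate the trial.

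**What to change.** Before outcomes are seen by arm:

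1. Define one primary attendance endpoint in all randomised patients: either one visit, with its time window, or a stated composite such as attendance at all scheduled visits. The investigators should justify the choice.
2. Test it at two-sided 0.05 with an analysis that accounts for week, for example a mixed model or GEE with a small-sample correction, or a week-level analysis.
3. State the assumed control rate for that endpoint, reconcile the two sample-size statements, and restate the power with an assumed ICC and cluster size.
4. State whether survey completion is secondary, or co-primary with its own alpha.
5. Label the other visits, EPP use and the race and income analyses secondary or exploratory, and report all of them.

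If outcomes by arm have already been seen, report all visits and label the choice of primary post hoc.

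The cost is some SAP wording and one power recalculation. A single primary keeps the full 0.05. The downsides are that an isolated positive result at a non-primary visit is no longer confirmatory, and that accounting for week lowers the stated power, from 79.8% to between 78.3% and 63.9% under the assumptions above.

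### One undated app survey may replace the clinic survey at 90 days, 1 year or both, mainly in the intervention arm, so survey completion at those visits has no common definition

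*Combined protocol and SAP*

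**What the plan says.** Aim 2 (Specific Aims) asks whether inpatient enrollment "improves survey completion rates after orthopedic trauma". It names no time point, window or denominator.

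The study procedures under Research Design and Methods contain three relevant statements.

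- App survey: "In the period between hospital discharge and follow-up, patients using the Gateway app will be requested to fill out a survey on their personal device". The same sentence adds that these patients "will receive a notification of their upcoming appointment". There is no due date, number of surveys or named visit.
- Clinic survey: "At 90 day and 1 year follow-up outpatient appointments, patients from both groups will be invited to complete a survey on a hospital owned tablet". The visits monitored are the "first, 90-day, and 1-year follow-up outpatient appointments", so the first visit has no tablet survey.
- Substitution: two satisfaction questionnaires follow the regular survey, but "if already completed over the app; just the satisfaction questions will be administered". There is no limit on the age of the app survey and no link to a particular visit.

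Every intervention patient is enrolled in the app with staff present. Controls only receive information on how to enroll.

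The section headed Statistical analysis, study size covers factors associated with follow-up and portal use. It does not mention survey completion or how a survey is assigned to a visit.

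**The concern.** Read together, the statements describe one app survey and two clinic occasions that it may displace. Staff who apply the substitution literally could omit the tablet survey at 90 days for a patient who answered on the phone shortly after discharge, and omit it again at 1 year. A control patient who never uses the app is offered the tablet survey at both visits.

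The analyst then has two ways to count, and the plan chooses neither. If the early app survey counts, the intervention arm may be credited with 90-day or 1-year completion although no survey was taken at that time. If only surveys taken at the visit count, the rule itself has removed some of them from that arm. In both cases part of the difference for Aim 2 comes from the substitution rule and not from any effect of the app on willingness to respond.

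**Working it through.** The documents give no rate or sample size for survey completion, so there is no planned figure to reproduce. The 240 patients are justified on clinic follow-up. The calculation below is an illustration that isolates the rule by giving the app no effect on attendance.

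Inputs:

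- a = 0.70, attendance in both arms. The 70% is the plan's assumed existing follow-up; equality between arms is assumed here.
- t = 0.80, tablet completion among attenders who are offered it (assumed).
- e = 0.20, share of app users who complete an early app survey, independent of attendance (assumed).
- u = share of controls who become app users: 0, then 0.40 (assumed). All intervention patients are taken as app users.
- The app survey is not sent again before the visit (assumed; the text is silent).

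**Tablet survey offered to everyone.** Completion is a × t = 0.70 × 0.80 = 56.0% in each arm, a difference of 0.

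**Rule applied, u = 0.**

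- Early surveys count: intervention e + (1 - e) × a × t = 0.20 + 0.80 × 0.56 = 64.8%; control 56.0%; difference **+8.8 points**.
- Only surveys taken at the visit count: intervention (1 - e) × a × t = 0.80 × 0.56 = 44.8%; control 56.0%; difference **-11.2 points**.

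**Rule applied, u = 0.40.** The share of controls with an early app survey is 0.40 × 0.20 = 0.08.

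- Early surveys count: control 0.08 + 0.92 × 0.56 = 59.5%; difference 64.8 - 59.5 = +5.3 points.
- Only surveys taken at the visit count: control 0.92 × 0.56 = 51.5%; difference 44.8 - 51.5 = -6.7 points.

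**Range.** In general the two differences are +e(1 - u)(1 - at) and -e(1 - u)at. With a = 0.70, e from 0.10 to 0.40, t from 0.60 to 0.90 and u from 0 to 0.40:

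- Early surveys count: from 0.10 × 0.60 × (1 - 0.63) = +2.2 to 0.40 × (1 - 0.42) = +23.2 points.
- Only surveys taken at the visit count: from -0.10 × 0.60 × 0.42 = -2.5 to -0.40 × 0.63 = -25.2 points.

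**Dependence on attendance.** Let q be the share of early app responders who would have attended and completed the tablet survey anyway. With u = 0 the differences are +e(1 - q) and -eq. Independence is q = 0.56. At q = 1 the inflation is 0, but the loss by the at-visit count is -20 points. At q = 0 they are +20 and 0. The gap between the two counts is e = 20 points whatever q is.

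**Dependence on timing.** If an app survey is sent shortly before each visit, few app surveys are early, e is close to 0 and both differences are small.

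**The case against.** The strongest reply is that the plan intends a pre-visit survey. The survey request shares a sentence with the appointment notice, and the substitution can mean only that a survey already done on the phone for this visit is not repeated on the tablet. The tablet survey also runs under a standard clinic protocol that is not among the documents and may settle the timing. This reading is possible, and under it the problem is small. But the text does not state it: three visits are monitored, the follow-up in question could be the first one, and a single survey is set against two clinic occasions.

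A reader might go further and infer that an app survey done at any time definitely cancels both later surveys, that the plan carries early responses forward, or that the arms are measured at different points in recovery. The documents do not support this.

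- The plan is silent on timing. It does not adopt an any-time rule, and no counting or carry-forward rule is written.
- The split between arms is not clean. Controls who enroll themselves fall under the same rule, and intervention patients who do not use the app are still offered the tablet.
- Aim 2 is a completion rate and no analysis of survey scores is planned, so the issue is unequal opportunity to be counted more than stage of recovery.
- Completing a survey away from clinic is partly the effect under study, so counting app surveys is not in itself bias.

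Larger figures are also easy to produce. With 85% v 70% attendance and 40% early app completion, counting early surveys gives 0.40 + 0.60 × 0.85 × 0.80 = 80.8% v 56.0%, or +24.8 points. Of that, 0.85 × 0.80 - 0.56 = 12 points is the assumed attendance benefit and not the rule.

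Finally, the form asks for a brief description and the sample size does not rest on surveys. That limits the weight of the point. It does not remove it, because survey completion is one of only two stated aims and the substitution determines which surveys are collected.

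**Conclusion.** The point holds in limited form. As written, one app survey without a date or named visit may replace the tablet survey at 90 days, 1 year or both, and this falls mainly on the intervention arm. No other section repairs it. Completion for Aim 2 may be credited without a survey from that time, or a later survey may be withheld by the rule.

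Neither the size nor the direction can be fixed from the documents. The central illustration, +8.8 or -11.2 points according to the count used, rests wholly on the assumptions listed and should not be read as an estimate of bias in this trial. What it shows is that an unstated choice can change the sign of the comparison. The plan should be changed on this point, but it does not touch the clinic follow-up aim.

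**What to change.** In the study procedures under Research Design and Methods:

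1. Request the app survey separately for the 90-day and the 1-year time points.
2. Omit the tablet survey only if the app survey for that same visit has been completed; otherwise offer the full survey in clinic.

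In the statistical section:

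3. Define completion per visit as a survey by either route dated within a pre-set window. Use the same window in both arms, and make it wide enough to include a survey taken at a late-attended visit.
4. Report earlier app surveys separately, so that out-of-clinic response is still visible as an effect of the app.

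The cost is protocol wording and an app survey scheduled per visit; the documents do not show whether the app can already do this. Some app users will answer again in clinic, and stated completion in the intervention arm may be lower. If surveys have already been collected under the present text, both counts can be reported from the survey dates, provided these were recorded, but tablet surveys that were not offered cannot be recovered.
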